**FORM: Application for Human Research**

NUMBER	FORM DATE	PAGE
F200	02/2014	25 of 39

2. N-Back Task. The n-back task is a widely used task in functional neuroimaging for probing working memory (Drobyshevsky, Baumann, & Schneider, 2006; Jansma, Ramsey, Coppola, & Kahn, 2000). Participants will continuously monitor a series of letters as they appear on a screen and will be required to indicate when a pre-specified target letter appears in the sequence. During the control portion of the task (0-back), the subject merely responds when the prespecified letter appears on the screen. During the experimental task (2-back), the subject responds when the current letter is the same as on displayed 2-letters previously. The task has been shown to reliably activate the dorsolateral prefrontal cortex (Drobyshevsky et al., 2006).

3. Resting State fMRI. Emerging evidence suggests that the brain shows stable patterns of functional connectivity during the resting state and that these patterns may be particularly useful in elucidating specific networks (Shehzad et al., 2009; Voss & Schiff, 2009; Zhang et al., 2008; Zhong et al., 2009). Therefore, subjects will also be scanned for 6 minutes with eyes closed and instructed to let their “mind wander.” Functional connectivity will be evaluated from pre- to post-treatment for the two groups.

4. (HC Arm Only) Food Activity Decision Task & Food Rating Task. This will be administered to subjects during MRI to determine foods subjects may find appetizing and if healthier or unhealthier choices are made. The FADT is done during the MRI in scanner and the FRT is done afterwards outside the MRI scanner.

**Modified Sleep Latency Test (MSLT)**

At each session, participants will undergo an MSLT with polysomnographic (PSG) recording. A trained technician will fit each participant with a standard electrode montage for PSG recording. Standard PSG will be recorded using an ALICE system. The participant will be escorted three times to a private sound attenuated bedroom where they will attempt to take a brief nap. Participants will be given up to 20 minutes to fall asleep. PSG recordings will be scored by a trained technician using Somnologica software to determine the latency to fall sleep.

**Six-Week Light Exposure Treatment**

At the conclusion of the assessment and scanning session, all main study arm participants will also be given a Phillips goLITE device and WattsUp? Pro® power usage meter. This is a power usage meter used to instantly display the wattage being used. This device is being used to measure wattage use for subjects to help track study compliance. The goLITE BLU is a commercially available device that provides controlled exposure to narrow band blue wavelength light with a peak wavelength of 464-467 nm. The device consists of a table-mounted, 13.5 x 14 cm plastic encased device with a 10-by-6 LED array. The WattsUp? Pro® power usage meter will be used in conjunction with the Phillips go LITE device to measure compliance. Specifically, the WattsUp? Pro® meter will be used to measure: times of day during which the Phillips goLITE device was used, duration of use, and intensity setting at which it was used. Participants will be given a demonstration about how to use the instrument and will also be provided with written instructions. Each morning, within 2 hours of awakening, but prior to noon each day, participants will use the light device for 30 minutes. This will allow added flexibility and reduce subject burden by permitting subjects the opportunity to choose

**FORM:** Application for Human Research

NUMBER	FORM DATE	PAGE
F200	02/2014	26 of 39

whether to use the light immediately upon arising, or after morning hygiene, meals, drive, etc., but will still ensure that all treatment occur in the morning hours. The instrument is equipped with a timer to ensure 30 minutes of exposure. Appropriate use will involve placing the light device at a distance between 12-24 inches, offset from center to reduce glare. Participants will be instructed not to look directly at the light source, but to allow the light to enter from their peripheral vision. Each morning, within 2 hours of arising from sleep, participants will 1) document the time, indicate sleepiness using the Stanford Sleepiness Scale (SSS), activate the light device, and document the sleep and wake times from the previous day. At the completion of the light period, participants will again indicate sleepiness using the SSS. To further monitor compliance, the wrist actigraph will also include a light monitor. Participants will be instructed to ensure that the light sensor of the actigraph is exposed to the light source for the full 30-minute duration in order to verify compliance. This will permit cross-verification that subjects have in fact used the blue wavelength light at the specified times (and will allow co-variation for additional light effects in statistical analyses). MBLT exposure will be conducted daily for 6-weeks for all participants. Participants will also be contacted weekly by phone to ensure compliance, answer questions, and collect a weekly Epworth Sleepiness Scale.

Half of the participants will be randomly assigned to the morning MBLT or a sham placebo light treatment (SPLT). Participants in the MBLT group will be administered blue light therapy using the standard goLITE BLU device, whereas participants in the SPLT group will be given identical appearing goLITE devices where the standard bright blue-wavelength LEDs have been replaced with amber LEDs. The goLITE BLU has been shown to have a narrow bandwidth, peaking at  $\lambda = 469$  nm, at 214 Lux, and panel irradiance  $\text{mW/cm}^2 = 1.23$  at 20 cm. A similar appearing amber LED system (goLITE AMBER) will be employed for the SPLT devices, but will peak at  $\lambda = 566$  nm, at 180 Lux, and total irradiance  $(\text{mW/cm}^2) = 0.58$ .

**Safety.** The Philips goLITE BLU device is a commercially available product marketed for relief of “winter blues” and improvement of mood. The device has been used off label for treatment of SAD and jet lag and has undergone extensive safety testing based on U.S. and international standards for photobiological safety of light devices. An independent optical safety analysis was provided to the manufacturer of the devices on 30 August 2009, and is attached as an appendix to this application. The analysis indicated that the averaged radiance of the array of LEDs is below hazardous standards set by the Illuminating Engineering Society of North America (IESNA) and the International Commission on Illumination, and International Electrotechnical Commission, and meets criteria for an Exempt product without photobiological risk when used as indicated.”

The goLITE AMBER units have lower total irradiance levels and include significantly less blue wavelength light than the blue active condition. A safety analysis was conducted on the AMBER lights (20 April 2006, attached) and these were found to pose no meaningful optical hazard when used as indicated. The safety analysis concluded that the emission levels of the amber device are so far below recommended safe exposure limits that even photosensitive individuals would not be at risk.

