**FORM: Application for Human Research**

NUMBER	FORM DATE	PAGE
F200	02/2014	9 of 39

laboratory and provide excellent resolution for evaluating functional changes within the target regions of the anterior cingulate gyrus, hippocampus, and prefrontal cortex. Furthermore, the proposed project will directly assess sleep functioning using actigraphy and correlate these changes in sleep with pre-to post-treatment changes in neurocognitive performance and symptom presentation, as well as functional activity changes.

Briefly, individuals who have experienced a mTBI, with or without loss of consciousness, as verified by a medical report, and who complain of sleep disturbance, will undergo an initial psychological assessment, and will be then fitted with an actigraph to wear for the duration of the study in order to measure baseline sleep as well as any changes in sleep patterns. Individuals will then return to complete two comprehensive neurobehavioral assessment and neuroimaging sessions (functional MRI, structural MRI/diffusion tensor imaging; DTI) separated by 6 weeks. During the intervening 6 weeks, participants will be randomly assigned to receive 30 minutes of morning blue light therapy (MBLT) or a sham placebo amber light treatment (SPLT) daily. Sleep quality and quantity will be measured via continuous wrist actigraphy monitors and self-report inventories.

For interested subjects participating in the last phase of recruitment, we will continue collecting wrist actigraphy and self-report data for an additional 6 weeks after completion of the baseline period and light therapy as an optional part of the study. It is hypothesized that MBLT will improve sleep quality and quantity relative to SPLT, and these improvements will be associated with changes in brain function, brain structure, and reduced post-concussion symptom severity at follow-up assessment.

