## FORM: Application for Human Research

NUMBER	FORM DATE	PAGE
F200	02/2014	19 of 39

consent during an initial assessment session and will then be scheduled for a baseline assessment/scanning session.

At baseline, participants will complete a comprehensive neuropsychological test battery, including personality and psychodiagnostic testing, a modified sleep latency test (MSLT), and will undergo two scanning sessions, including 3T fMRI, structural MRI, and DTI scans.

Over the next 7 weeks, participants will wear a wrist actigraph for sleep monitoring and complete daily sleep diaries. During the 6 weeks between the second and third session participants will use a commercially available light therapy device for 30 minutes daily, within 2 hours of awakening, but prior to 10:30 A.M. each day. Subjects will be contacted by phone about once per week for a brief follow up to make sure that everything is progressing well and to answer any questions that arise.

After the treatment period, participants will return for a follow-up assessment/scanning session similar to that conducted at baseline.

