### Initial Assessment

Upon arrival, all participants will have the procedures thoroughly explained and will complete verbal and written informed consent procedures. Participants will complete the Mini-International Neuropsychiatric Interview (MINI), the Screen Time Questionnaire, Personality Assessment Inventory (PAI), the Wechsler Abbreviated Scale of Intelligence II (WASITM II) as a measure of

**FORM:** Application for Human Research

NUMBER	FORM DATE	PAGE
F200	02/2014	20 of 39

intelligence and the VA National Traumatic Brain Injury Neurobehavioral Symptom Inventory (NSI). The first visit is still considered part of the initial screening portion of the study and the subject's responses to the assessments and questionnaires will be evaluated to determine his or her eligibility for subsequent portions of the study. For example, if significant psychopathology or other disqualifying condition is discovered during the psychiatric assessment or if it becomes evident that the participant is unable or unwilling to comply with study procedures, research study staff may withdraw that individual from the study. If the participant is deemed ineligible for continuation, compensation will be provided for the time he or she participated according to a prorated schedule. At the conclusion of the initial assessment, eligible participants will be fitted with a wrist actigraph (Actiwatch AW-Spectrum) for measuring sleep-wake patterns and trained in its use. In addition, participants will be given a sleep diary to be completed upon awakening each morning. Subjects will wear the wrist actigraph and complete sleep diaries and scales for the week prior to their baseline assessment/scanning session.

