**FORM: Application for Human Research**

NUMBER	FORM DATE	PAGE
F200	02/2014	27 of 39

activity levels and sleep 24 hours a day. This data can then be analyzed via sleep analysis software (Actiware 5®) that includes algorithms that transform activity data into probable sleep periods. The Actiwatch also includes three color light sensors that provide irradiance and luminous lux recordings in three color bands of the visible spectrum, including red, green, and blue. The light sensor will be used to verify that subjects are in fact undergoing the daily light treatment and will permit covariation of other daily light sources in the statistical analyses. The device also records periods of off-wrist time to determine compliance. Data will be downloaded using the Actiwatch-2 communication dock after week 7 of the study.

Participants will also keep a daily sleep log during the 7-week period.

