**I. BIOSTATISTICAL ANALYSIS**

Several global outcomes and their interpretations include:

- 1) “If the effects of MBLT versus SPLT are not different and improvement is observed in both groups”—this would suggest that nonspecific effects (practice, maturation, recovery) occurred but were unrelated to the MBLT treatment. Thus there is no specific benefit to the use of MBLT versus placebo. Based on such an outcome, there would be no recommendation for the use of MBLT for treatment of post-concussive symptoms. Secondary analyses correlating cognitive/symptom improvement with changes in brain structure and function may identify new avenues of research and would still contribute valuable knowledge regarding these relationships.
- 2) “If effects of MBLT versus SPLT are not different and no significant improvement is observed in either group”—this finding is less likely, as continued improvement between the two sessions would be expected due to gradual recovery during the first year and due to practice effects associated with repeated assessment. While such a finding would clearly suggest that there is no specific benefit to the use of MBLT versus placebo, it would raise suspicion that the assessments were invalid or insensitive.
- 3) “If MBLT is better than SPLT”—this is the hypothesized effect. This would support the hypothesis that MBLT is beneficial in the treatment of post-concussive symptoms relative to placebo. Regression analysis between the change in symptoms/neurocognitive function and measures of sleep and mood would identify whether this was due to sleep related changes or whether the changes were due to the mood altering effects of MBLT, or both. Similarly, changes in one condition and not the other will also be examined for their relationship to

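### Could covariate adjustment for actigraph light recorded during treatment distort the comparison of blue with amber light?

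*Combined protocol and SAP*

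**What the plan says.** The light covariate is mentioned twice, both times in Section 3, item 7.

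- Six-Week Light Exposure Treatment: after explaining that the actigraph's light sensor helps confirm lamp use, the text adds in parentheses that the record "will allow co-variation for additional light effects in statistical analyses".
- Actigraphic Sleep Measurement: after the same point about verifying treatment, it adds that the sensor "will permit covariation of other daily light sources in the statistical analyses". It then says "Data will be downloaded using the Actiwatch-2 communication dock after week 7 of the study".

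On timing, Initial Assessment says "Subjects will wear the wrist actigraph and complete sleep diaries and scales for the week prior to their baseline assessment/scanning session". The procedures overview says "During the 6 weeks between the second and third session participants will use a commercially available light therapy device". The seven-week record is therefore one week before the lamp and six weeks with it. The overview mentions seven weeks of wear only after it describes baseline, but Initial Assessment is explicit that the first week precedes the baseline session.

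I. Biostatistical Analysis describes four possible results. If MBLT does better than SPLT, it says "This would support the hypothesis that MBLT is beneficial in the treatment of post-concussive symptoms relative to placebo". It then proposes "Regression analysis between the change in symptoms/neurocognitive function and measures of sleep and mood" to explore mechanism. It names no primary outcome, no model for the arm comparison and no light covariate.

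**The concern.** Light recorded after the lamp is issued is a post-randomisation measurement. The Background expects blue light to advance the circadian phase, improve sleep and raise daytime alertness. Someone who wakes earlier and is more alert may well get different amounts of ordinary light at different times. Non-lamp light could then lie on the path from treatment to outcome, or share unmeasured causes with outcome. Conditioning on it would remove part of the effect or add bias, in either direction.

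Light is also the only covariate the form foresees for the arm comparison, since sleep and mood appear only in the mechanism regression. Nothing confines it to the week before the lamp or to secondary analyses. At stake is whether the reported MBLT–SPLT difference is the total effect of assignment.

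**Working it through.** The plan has no figure of its own to reproduce. The form as seen gives no test level, power, effect size or SD for MBLT versus SPLT.

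**Input from the form.** 30 complete datasets (Study Population), half allocated to each light, so 15 per arm.

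**Assumed inputs.**
- a, the arm difference in treatment-period non-lamp light in within-arm SD units: −0.6 to +0.6.
- r, the within-arm correlation of that light with outcome: −0.4 to +0.4.
- Within-arm outcome SD of 1, a two-sided 5% t-test, and a true effect of 0 or 0.5 SD.

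**Bias.** In a linear model the light-adjusted arm coefficient is the total effect minus a × r, so bias = −a × r. The unadjusted standard error is √(2/15) = 0.365.

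| Size of a | Size of r | Size of bias (SD) | Bias / SE | Rejection, true effect 0 | Rejection, true effect 0.5 |
|---|---|---|---|---|---|
| 0 | any | 0 | 0 | about 5% | no bias |
| 0.3 | 0.2 | 0.3 × 0.2 = 0.06 | 0.06/0.365 = 0.16 | about 5.2% | 21% or 31% |
| 0.6 | 0.4 | 0.6 × 0.4 = 0.24 | 0.24/0.365 = 0.66 | about 10% | 11% or 52% |

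Rejection rates come from 100,000 simulated trials per setting. The unadjusted comparison rejects about 26% of the time at 0.5 SD. The two figures in the last column depend on the sign of a × r.

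**Precision if treatment does not shift other light (a = 0).** The adjusted SE is √(2/15) × √(1 − r²) × √(27/26):
- r = 0.4: 0.365 × 0.917 × 1.019 = 0.341, a reduction of 6.6%.
- r = 0.2: 0.3645, a reduction of 0.2%.

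**Would a rule restricting the covariate to pre-lamp light help?** Assume pre-lamp light correlates 0.5 with later light, so its correlation with outcome is 0.5 × r. The same formula gives 0.3645 at r = 0.4 and 0.3702 at r = 0.2, against 0.3651 unadjusted. It is unbiased but gains almost nothing, and at r = 0.2 it loses slightly.

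**What the text commits to.** Both sentences follow statements about checking that the lamp was used. Both say what the record makes possible, not what will be fitted. The words additional and other show that lamp light is not the intended covariate, and the power meter logs times of lamp use, so lamp minutes can be set aside. The section that interprets the arm comparison does not mention light.

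**The case for a change.** The strongest opposing case is that permissive wording is the problem. An analysis plan should settle before data are seen whether to adjust and over which weeks, and one sentence would do it. The assumed ranges may also be too narrow. In a separate simulation of 8,000 trials per setting with a true effect of 0.80 SD, a light shift of 0.5 SD and a light–outcome slope of 0.3 took the adjusted estimate to 0.65, with rejection falling from 0.57 to 0.40. A shift of 1.0 SD and a slope of 0.5 took it to 0.29. A shift of −0.5 SD with slope 0.3 raised it to 0.95.

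The principle stands: a treatment-affected covariate does not belong in an estimate of the total effect, and the form does not say so. What does not stand is the step from there to a fault in this plan. The form nowhere predicts an arm difference in non-lamp light. Both arms follow the same 30-minute morning routine, and people on shift work or markedly late sleep schedules are excluded, which limits large differences. The larger biases need large shifts and strong associations together, all of them assumed.

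The form also lists a separate protocol and a grant application as attachments. Neither was available, so it cannot be said that the point is unsettled elsewhere.

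**Conclusion.** The concern is sound as a caution but calls for no change. Followed as written, the plan commits to no biased analysis: it notes that light data could serve as a covariate and attaches that covariate to no outcome, model or arm contrast. The missing covariate policy is a small part of a wider silence about the primary outcome and main model. Whoever writes that model settles its covariates with it, and leaving post-randomisation light out of the main comparison is ordinary practice. The light record remains useful for compliance and for exploratory or mediation work.

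The size is conditional and cannot be computed from the documents. It is zero if treatment leaves other light unchanged, 0.06 SD (0.16 SE) in the middle of the assumed ranges, and 0.24 SD (0.66 SE) at the extreme of both, with unknown sign. These figures rest on 15 per arm, which follows from the form, and on assumed values for the light shift, its correlation with outcome, the two-sided 5% test and the 0.5 SD effect. Prescribing pre-lamp light as the covariate would bring almost no precision.

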**FORM: Application for Human Research**

NUMBER	FORM DATE	PAGE
F200	02/2014	11 of 39

the same room for the full 60 minutes. During the 30 minute wash out and 30 minute light exposure periods, subjects will be asked to sit quietly for 10 minutes and fixate on a large cross opposite them in order to help get clean EEG data. During this time, their EEG (electroencephalography) will be recorded via leads attached to the subject's scalp to help measure brain activity. It must be noted that because subjects will see the color of light they will be exposed to, it is impossible to blind subjects to the condition. Hopefully, subjects will not be to knowledgeable about the effects of various wavelengths of light. Following this, participants will get into the fMRI scanner and will undergo a series of tests of attention, concentration, memory, and other cognitive abilities (CVLT II, MSIT, N-Back, BMAT, Anticipation Task), and will complete clinical measures to assess mood. Subjects will have their heart rate monitored via EKG during baseline and post treatment visits only. Subjects will complete several post-scan tests and questionnaires including the PANAS to conclude their participation. Over the course of the initial visit, subjects will also have 3 saliva collections to measure their melatonin levels. Before concluding their initial visit, subjects will be given and instructed in the use of an Actiwatch device to wear until their follow-up visit the same day.

Subjects will be asked to return for a follow-up visit at approximately 8:30pm the same day to collect a fourth and final melatonin sample as well as return the Actiwatch.

In this study, we will use functional and structural brain imaging techniques such as functional magnetic resonance imaging (fMRI) and diffusion tensor imaging (DTI) to evaluate brain function and brain structure. Identifying and mapping the brain systems before and after light exposure may help researchers develop further insights into the relationship between concussion, light exposure, sleep, and brain function and will provide brain targets for study in the analysis of the Main Study Arm.

Please note that all cognitive testing, questionnaires, and MRI/fMRI scanning for this healthy control arm are akin to the main arm of this study.

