#### **5) Study Population**

##### **Main Study Arm:**

**FORM: Application for Human Research**

NUMBER	FORM DATE	PAGE
F200	02/2014	14 of 39

Forty (40) individuals between the ages of 18 and 50 with a documented history of a “concussion” or mTBI in the preceding 18 months but no sooner than 4 weeks prior to the screening will be recruited to participate in the main study arm. It is anticipated that approximately 6 participants (i.e., 17%) will withdraw early or fail to comply with procedures. Thus, a total of 40 participants will be run to achieve a total sample size of 30 complete datasets. The occurrence of a concussion or mTBI must be documented by a medical/objective professional (e.g., sports trainer, coach, physician, nurse, etc.) report. In addition, at least half of the participants recruited for each condition will be required to have complaints consistent with sleep onset insomnia (i.e., trouble falling asleep) as measured by Insomnia Severity Index (ISI) or delayed sleep phase disorder (i.e., not feeling sleepy at bedtime and/or not able to fall asleep until much later than bedtime). Participants with a lifetime history of head injury leading to loss of consciousness greater than 30 minutes will be excluded. Other exclusion criteria will include any current medical condition that would be contraindicated for scanning, other known neuropathology (e.g., tumor, neurodegenerative disease, normal pressure hydrocephalus, etc.), abnormal visual acuity that is not corrected by contact lenses, metal within the body, or time since injury exceeding 18 months.

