**Post-Treatment Assessment and Scan:**

At the completion of 6-weeks of MBLT or SPLT, participants will return to the laboratory and turn in the light device. Participants will undergo a comprehensive neurocognitive assessment virtually identical to the pre-treatment assessment. A series of functional and structural neuroimaging scans will be repeated to evaluate the impact of treatment on brain function and structure. Finally, in order to provide an objective measure of sleep latency, an MSLT with polysomnography will be performed at the same time of day as during the first visit.

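### No masking of main-arm outcome testers or scorers is described, and routine steps can reveal lamp colour to them; MSLT latency and RBANS are exposed, and task order and file handling would repair it.

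*Combined protocol and SAP*

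**What the plan says.** In the main arm, half the participants are randomised to a blue lamp (MBLT) and half to an amber sham (SPLT), used at home every morning for six weeks (Section 3, item 7, Six-Week Light Exposure Treatment). The housings match and the LEDs differ in colour.

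Four routine steps touch on lamp colour:

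- **Issue.** The lamp is handed over once baseline testing and scanning are finished, with a demonstration. Item 8 (Risks to subjects) adds that this is interactive and that the participant practises the viewing position.
- **Calls.** "Participants will also be contacted weekly by phone to ensure compliance, answer questions, and collect a weekly Epworth Sleepiness Scale".
- **Return.** After six weeks, "participants will return to the laboratory and turn in the light device" (Post-Treatment Assessment and Scan). The same paragraph then describes repeat testing, scanning and the MSLT.
- **Actigraph.** Participants are told to keep the watch's sensor exposed to the lamp throughout each session. "The Actiwatch also includes three color light sensors that provide irradiance and luminous lux recordings in three color bands of the visible spectrum" (Actigraphic Sleep Measurement).

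Two outcomes depend on staff. For the MSLT, "PSG recordings will be scored by a trained technician using Somnologica software to determine the latency to fall sleep". For RBANS Semantic Fluency, the study team writes down the answers, checks them against audio on the same day, and then erases the audio (Neurocognitive Assessment).

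The only explicit blinding statement is in the Lay Summary and concerns healthy-control subjects: "it is impossible to blind subjects to the condition". No statement about masking of testers, scorers or callers in the main arm was found in the supplied text.

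**The concern.** Main-arm participants see the colour of their lamp every morning, even if they may not know which colour is active. Self-reported sleep and mood can therefore carry expectation. Outcomes that rest less on the participant's beliefs matter more, and where those outcomes need human judgement, masking the staff is what protects them.

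The Biostatistical Analysis section names MBLT superiority as the hypothesised result, so staff who know the arm know which way the result is expected to go. The MSLT is introduced in the Post-Treatment section as the objective measure of sleep latency. If its scorer, or the RBANS examiner, could have known the arm, a reader can discount an MBLT advantage on those measures. A consistent scoring shift of this kind does not average out with more participants.

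**Working it through.** **1. What each step can reveal, and what the text leaves open**

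| Step | What it can reveal | What is not stated |
|---|---|---|
| Demonstration at issue | Colour, if the lamp is lit while viewing is practised; the most direct route | Who demonstrates |
| Weekly call | Colour only if it comes up in conversation | Who calls |
| Return at the third visit | Colour, if visible or mentioned | Who receives it; whether an unlit lamp shows its colour; whether the listed order is binding |
| Actigraph colour channels | A daily morning blue or amber signal in the record used for sleep | Who opens the record; whether channels are hidden |

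**2. Which outcomes this can reach**

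| Outcome | Room for staff judgement |
|---|---|
| MSLT latency | Yes: scored by a technician. No light channel is described in the polysomnography, so the route is contact with the lamp or the arm list |
| RBANS | Yes: testing is in person and staff record the spoken fluency answers. Once the audio is erased, masked rescoring of Semantic Fluency is impossible |
| Actigraphic sleep | Only if intervals are edited by hand; the text describes a software algorithm and mentions no editing |
| ANAM4 | Little: can be self-administered on a computer |
| PVT | Little: computer task scored as mean reaction time |
| ESS | Self-report, so scorer masking adds little |

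**3. Illustration of size**

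The documents give no alpha, SD, effect size or primary endpoint, so there is no planned figure to reproduce. The inputs are:

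- Sample size: "Thus, a total of 40 participants will be run to achieve a total sample size of 30 complete datasets" (Study Population). With equal arms, 30/2 = 15 per arm.
- Assumed: two-sided alpha of 0.05, two-sample t test, no true effect, and a constant shift of b SD in favour of MBLT.

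Standard error of the difference in SD units: sqrt(2/15) = 0.365. A shift of 0.1 SD is 0.1/0.365 = 0.27 standard errors, and 0.3 SD is 0.3/0.365 = 0.82.

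The rejection rate comes from the noncentral t distribution with 2 × 15 − 2 = 28 degrees of freedom and noncentrality b × sqrt(15/2):

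| Assumed shift b (SD) | Two-sided rejection rate | Share falsely favouring MBLT |
|---|---|---|
| 0 | 5.0% | 2.5% |
| 0.1 | 5.8% | 4.5% |
| 0.2 | 8.3% | 7.6% |
| 0.3 | 12.5% | 12.2% |

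A larger sample does not help. The plan also says "It is anticipated that approximately 6 participants (i.e., 17%) will withdraw early or fail to comply with procedures", which would leave 40 − 6 = 34 completers, or 17 per arm. The same shifts of 0.1, 0.2 and 0.3 SD then give 5.9%, 8.7% and 13.6%.

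**The case against.** The case on the other side is substantial.

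- No section assigns lamp issue, calls or lamp return to the people who test or score. A phone call shows no colour, and the ESS collected in it is self-report.
- The two lamps are described as alike in appearance, so an unlit lamp may reveal nothing. Return and testing stand in successive sentences, which need not fix their order.
- Records already carry an ID number only, and the linking file is limited to the principal investigator and project coordinator (item 10). The same-day RBANS audio check limits selective transcription.
- Section 4 lists a separate protocol and a treatment schema that are not in the supplied text. Either might mask assessors.
- The staff in item 4 serve the whole laboratory, and no rota is given. Testing and scanning are at different locations.

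Much of this stands. A reader might infer that the routine actually shows lamp colour to those who score outcomes. The text does not support that; it shows opportunities and no separation of roles. A reader might also infer that the trial has no bias-resistant outcome. That is contradicted by ANAM4, which is named in the primary aims, and by the PVT, both of which leave little to an assessor.

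The objection does not supply the missing safeguard. An ID code hides the person and does not by itself hide the arm. The audio check verifies what was said, but it is made by the study team without stated masking. Matching housings do not cover a demonstration in which the lamp is lit.

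**Conclusion.** The point holds in a limited form. The supplied text masks no main-arm tester or scorer, and its routine can reveal the arm to them. MSLT latency and RBANS are open to assessor bias. Actigraphy is open only if sleep intervals are edited by hand, and ANAM4 and PVT are little affected.

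The size is unknown. The range of 0.1 to 0.3 SD, with its 5.8% to 12.5% false-positive rate at 15 per arm, is an assumption chosen to show scale and not an estimate. The true shift could be near zero, and its direction is presumed from the stated hypothesis. The conclusion also assumes that the attachments not supplied contain no masking provision; if they do, a cross-reference would settle it.

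This is an inexpensive improvement that has to be in place before outcome testing. It does not invalidate the design.

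**What to change.** 1. **Separate roles.** Whoever demonstrates, issues and receives the lamp, and makes the compliance calls, does not do post-treatment RBANS testing or MSLT scoring for that participant. State this under Neurocognitive Assessment and MSLT.
2. **Lamp return.** The lamp comes back in a closed bag, either after testing or directly to that lamp handler.
3. **File handling.** Polysomnography is scored under the ID only, without access to the arm list. Actigraph colour channels are withheld until sleep variables are locked, then opened for the compliance check and the light covariates. The higher final payment in item 12 ($1,000 rather than $900) depends on evidence of lamp use, so any check needed before the lock should be made by the lamp handler.
4. **Arm list.** Restrict it in the same way as the ID file in item 10. Those who hold it should not score.

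Sample size, assessments and treatment are unchanged. Item 4 lists at least two full-time technicians and one full-time postdoctoral associate, so the separation is plausible with current staff, although no rota proves it. The cost is some scheduling care, including for lamp return across separate testing and scanning locations. Whether the actigraphy software can hide the colour channels is not documented. If it cannot, the lamp handler could prepare an export without them.
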